8.5.9 Guidelines for reporting product complaints

Any defect in the IMP must be reported as soon as possible by the Investigator to the monitoring team that will complete a product complaint form within required timelines.

Appropriate information (eg, samples, labels or documents like pictures or photocopies) related to product identification and to the potential deficiencies may need to be gathered. The Investigator will assess whether or not the quality issue has to be reported together with an AE or SAE.

8.6 PHARMACODYNAMICS

Pharmacodynamic parameters are not evaluated in this study.

8.7 BLOOD SAMPLE FOR EXPLORATORY RESEARCH

Venous blood samples will be collected to obtain whole blood, serum and plasma to be stored for possible future exploratory research (see [Section 8.8](#)), including genetic research.

A total of approximately 12 to 15 mL venous blood will be collected per each timepoint specified in the SoA ([Section 1.3](#) and [Section 1.4](#)) and split as follows

- 3 mL whole blood sample for DNA (K2 EDTA tube, collected at baseline only)
- 2.5 mL whole blood for RNA (Paxgene RNA collection tube)
- 4 mL whole blood for plasma
- 5 mL whole blood for serum

Storage tubes will be labelled and stored under appropriate conditions.

Blood samples for exploratory research will be collected from participants who have consented to participate in the exploratory analysis component of the study. Participation is optional. Participants who do not wish to participate in the exploratory research may still participate in the study.

Details on collection, storage and shipment of these samples will be provided in the study reference manual.

Blood samples will be collected as specified in the SoA ([Section 1.3](#) and [Section 1.4](#)).

See Appendix 5 ([Section 10.5](#)) for information regarding genetic research.

8.8 USE OF BIOLOGICAL SAMPLES AND DATA FOR FUTURE RESEARCH

Future research may help further the understanding of disease subtypes, disease biology, related conditions, drug response and toxicity, and can help identify new drug targets or biomarkers that predict participant response to treatment. Therefore, data and biological samples will be stored

and used for future research (“research substudy”) when consented to by participants (see [Section 10.1.3](#)) unless prohibited by local laws or IRBs/IECs (in such case, consent for future use of sample will not be included in the local ICF).

Blood samples (see [Section 8.7](#)) are explicitly collected for the purpose of future research. In addition, while skin biopsies will be collected and processed for the intended use described in [Section 8.3.1](#) these studies may not require the entirety of the tissue or processed material. With the participants separate consent, blood samples and any residual skin material remaining from planned laboratory work will be used for additional exploratory research (“research substudy”) related to atopic dermatitis and related inflammatory diseases such as asthma and hidradenitis suppurativa, atopic disease processes, interleukin pathway biology, additional drug safety assessments or development and validation of bioassay methods beyond those defined in the present protocol.

Analyses of blood and skin samples may include isolating DNA, RNA, proteins or metabolites for pharmacogenetic/genomic analysis, RNA transcriptomics (including whole transcriptome RNA sequencing), proteomics, metabolomics or lipidomics. DNA/RNA isolated from these samples will be used only to determine a possible relationship between genes and response to treatment with dupilumab, possible side effects to dupilumab and/or to study genes that may potentially be involved in atopic dermatitis and related inflammatory pathways.

Exploratory analyses may include isolation and analysis of DNA and RNA using whole genome, exome, transcriptome or targeted sequencing, or related technologies. If future research on genetic material is performed, this will also be limited to the purpose of addressing research questions related to the drug, the mechanism of action, the disease or its associated conditions. Additional proteomic analysis will utilize techniques such as enzyme-linked immunosorbent assay, Olink, mass spectrometry or related protein quantification technologies, to characterize the protein changes associated with dupilumab treatment, with AD disease conditions, or to understand related inflammatory pathways. Finally, metabolites such as lipids and other small molecules may be characterized using mass spectrometry or nuclear magnetic resonance spectroscopy.

The handling of genetic data is described in Appendix 5 ([Section 10.5](#)).

Each study participant will be informed by the Investigator about the purpose and objectives of the research substudy including future use sample storage, research analyses, and the use of coded data. In addition, each participant has to sign a separate informed consent form for the research substudy-related to future use of samples and research, and will also receive a written subject information explaining the matter.

In the event future research is conducted for other purposes, the study participants will be informed of those purposes and will be given means to object to those research projects.

Participants will be told that participation in this research substudy (use of samples for additional, exploratory research) and the use of their coded data for this purpose is optional and that they are free to refuse to participate and may withdraw their consent at any time and for any reason during the storage period. In that case, biological samples will be destroyed and coded data already available will be anonymized unless otherwise required by applicable laws. Data and samples will

be used in compliance with the information provided to participants in the ICF dedicated to future research and the research substudy.

Participants who decline to participate in this optional research substudy will not provide this separate signature but are still allowed to participate in the main part of the study.

All study participant data and samples will be coded such that no participant direct identifiers will be linked to them. If required by local regularities, all participant's data and samples required for DNA or RNA transcriptome analysis will be double coded following collection of samples. Coded data and samples for additional exploratory research will be transferred to and stored by an US based central laboratory vendor chosen and contracted by the Sponsor. The Sponsor adopts safeguards for protecting participant confidentiality and personal data (see [Section 10.1.4](#)).

The samples will be stored for a maximum of 15 years after the end of the study. Any samples remaining at the end of retention period will be destroyed. If a participant requests destruction of his/her samples before the end of the retention period, the Investigator must notify the Sponsor (or its contract organization) in writing. In such case, samples will be destroyed and related coded data will be anonymized unless otherwise required by applicable laws.

Study participant coded data will be stored for future research for up to 25 years after the end of the study. If data are still considered of important scientific value after this period, coded data already available will be anonymized unless otherwise required by applicable laws (the same will apply to the data of a study participant who has requested the destruction of his/her samples).

Participant's coded data sets provided to researchers for a specific research project will be available to the researchers for a maximum of 2 years after the end of their specific project (end of project is defined by publication of the results or finalization of the future research project report).

9 STATISTICAL CONSIDERATIONS

9.1 STATISTICAL HYPOTHESES

No formal hypothesis testing is predefined in this exploratory study.

9.2 SAMPLE SIZE DETERMINATION

Sample size for this exploratory study was determined based on medical experts' input/clinical judgement. No formal sample size estimation was conducted. Approximately 10 to 12 evaluable AD participants per site might be enough to provide interpretable data and meet study primary objective.

Neuronal architecture and neuromarkers data collected from skin biopsy in similar settings as planned for this study were not available: ie, expected changes from baselines in neuronal architecture and neuromarkers after 16-week treatment with dupilumab in AD participants with chronic pruritus are unknown.

Allowing for a drop-out rate of 20%, a total of approximately 34 AD participants with chronic pruritus will be enrolled to achieve a minimum of 12 evaluable AD participants per country, ie, participants with no major or critical deviations related to IMP and/or biomarker measurements, for whom the biomarker data for primary analysis, ie, neuronal architecture and neuromarkers data from skin biopsy at baseline and Week 17, are considered sufficient and interpretable.

Up to 10 healthy participants (with a minimum of 3 per country) serving as a reference comparator group will be enrolled. Healthy participants will be matched with AD participants, as far as possible, according to site, age, gender, race, location of targeted lesional and non-lesional skin area.

Drop-out rate in healthy participants is expected to be minimal.

Any drop-out participant will not be replaced.

9.3 POPULATIONS FOR ANALYSES

The following populations are defined ([Table 3](#)):

Table 3 - Populations for analyses

| Population | Description |
|-----------------------|--|
| Enrolled | All participants who sign the ICF |
| Intent-to-treat (ITT) | All enrolled patients, who received at least 1 dose of IMP and all enrolled healthy participants who have at least 1 skin biopsy performed, irrespective of compliance with the study protocol and procedures. |

| Population | Description |
|---------------------|---|
| Modified ITT (mITT) | All ITT participants. If prohibited therapies for AD (see Section 6.5.3) are used and assessed by the study team as having a significant impact on skin biopsy assessment, only visits prior to rescue treatment use are considered. |
| Safety | The safety population includes all patients, who actually received at least 1 dose of IMP or had at least 1 skin biopsy and all healthy participants who had a skin biopsy or another safety assessment performed |

Abbreviations: AD: atopic dermatitis, ICF: informed consent form; IMP: investigational medicinal product; ITT=intent-to-treat, mITT: modified ITT.

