- b Participants who discontinue the study treatment prematurely the end of treatment (EoT) assessments will be performed at the time of discontinuation to assure a complete clinical assessment in close temporal proximity to the premature termination of study treatment. In addition, to allow assessment of participant outcomes over the stipulated study period, participants will be asked and encouraged to complete all remaining study visits and participate in all assessments according to the visit schedule.
- c Electronic diary will be dispensed to the patients at Screening Visit (V1) and will be collected on Week 21 (Visit 6). The PROs will be administered to patients via eDiary. Patients will bring the eDiary to the site at each visit, and it will be reviewed and dispensed back to patients at each visit.
- d For future use and exploratory research; collection is optional; whole blood sample for DNA extraction will be collected at baseline only.
- e Biopsy (4 mm). Skin biopsy in AD participants will be collected in lesional tissue, with acute lesions. Excluding oozing, infections and chronic stages - lichenification. Preferably in the forearms followed by back.
- f Post-lesional healed or healing skin should localisation matched to the baseline pruritic lesional biopsy; if post-lesional healed skin that is completely non-pruritic non-lesional is not available at later visits, one of the following biopsies should be collected (in the order of relevance): 1. lesional non-pruritic skin, 2. Post-lesional pruritic skin or 3. lesional pruritic skin
- g Optional.
- h The IMP will be administered every 14 ± 2 days (Q2W) during the 16-week treatment period.
- i Self administration by AD patients or caregivers at home.
- j Whole blood sample collected at baseline and stored during the study for potential analysis if deemed necessary for safety reasons. Will be described in study reference manual.
- k Vital signs, including heart rate, systolic and diastolic blood pressure (mmHg), and body temperature (°C) will be measured.
- l Urine pregnancy test could be performed at home with or without the assistance of a home care provider. In case of positive urine test the study treatment will be withheld and a serum pregnancy test should be performed as soon as possible, to confirm the pregnancy. Pregnancy will lead to definitive treatment discontinuation in all cases.
- m Participants self assessment.

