6.5.1 Rescue medicine

During Treatment Period, if medically necessary (ie, to control intolerable AD symptoms on face and genital areas), rescue treatment for AD may be provided to participants at the discretion of the Investigator (ie, topical treatment with high potency topical corticosteroids [TCS]). Investigators should make every attempt to conduct efficacy and safety assessments (eg, disease severity scores, safety laboratory assessments) immediately before administering any rescue treatment. An unscheduled visit may be used for this, if necessary.

Investigators will be required to perform an IGA evaluation prior to starting rescue treatment and initiate rescue treatment only in patients who either have an IGA score of 4, or have intolerable AD symptoms. The date and time of rescue medication administration as well as the name and dosage regimen of the rescue medication must be recorded in the eCRF.

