8.1.1 Patient-reported outcome (PRO) scales

8.1.1.1 Peak pruritus assessed by numeric rating scale (NRS)

The Peak Pruritus NRS is a simple assessment tool that patients will use to report the intensity of their pruritus (itch) during a daily recall period. Patients will be asked to rate their worst itch on a 0 (“No itch”) to 10 (“Worst itch imaginable”) NRS by answering the following question: “On a scale of 0 to 10, with 0 being ‘no itch’ and 10 being the ‘worst itch imaginable’, how would you rate your itch at the worst moment during the previous 24 hours?”

The peak pruritus NRS has been already validated in AD adult patients; a threshold for clinically relevant, within-person response was found to be ≥ 2 to 4-point change (10).

Peak pruritus NRS will be assessed daily during the first 28 days of treatment and weekly from Day 29 onwards until EoS period (see [Section 1.3](#)).

The Pruritus NRS will be provided in the study reference manual.

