9.4.7 Description of efficacy variables

Efficacy parameters are described in [Section 8.1](#). The derivation of baseline results is described in [Section 9.4.3.2](#).

The analysis of the efficacy markers will be based on the mITT population. As a sensitivity analysis, the primary endpoint will also be analyzed based on the intent-to-treat (ITT) population. Secondary endpoints analysis might be run on the ITT population as sensitivity analysis in case an important number of patients using rescue therapy is observed.

Sub-group analyses might be done, if deemed appropriate.

If relevant, based on results obtained on planned analyses (eg, if any trend or signal is observed), further exploratory analyses could be conducted, using statistical models for instance.

Analysis

Table 4 - Efficacy analyses

| Endpoint | Statistical analysis methods |
|------------------|--|
| Primary | 
Change from baseline on Week 17 for intraepidermal nerve fiber density by PGP9.5 antibody staining in lesional skinChange from baseline on Week 17 for intraepidermal nerve fiber branching by PGP9.5 antibody staining in lesional skinRaw data and change from baseline to Week 17; ie, absolute and percent changes, will be summarized with descriptive statistics (such as mean, median, SD, minimum, maximum, and 90% confidence interval) and plots for AD participants based on the mITT population |

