1.2.6.2 Secondary endpoints

To analyze the changes from baseline on Weeks 3 and 21 for intraepidermal nerve fiber density and branching by PGP9.5 antibody staining in lesional skin, the summary plots for AD participants based on the mITT population (and on the ITT population, if applicable) will be graphs of mean +/- SEM for raw data, absolute and percent change from baseline at baseline (ie, 0), Week 3 and Week 21.

To analyze the changes from baseline on Weeks 3 and 21 for intraepidermal nerve fiber density and branching by PGP9.5 antibody staining in lesional skin and changes from baseline over time and at Weeks 17 and 21 for the outcomes of the assessments/questionnaires (peak pruritus assessed by numeric rating scale (NRS), eczema and severity index (EASI), scoring atopic dermatitis (SCORAD), patient-reported outcomes measurement information (PROMIS-itch), patient oriented eczema measure (POEM), dermatology life quality index (DLQI), atopic dermatitis control tool (ADCT) and sleep quality/skin pain/skin sensitivity/skin burning NRS), the individual profiles over time will be spaghetti plots on raw data with all the AD participants on the same graph and the AD group mean.

To analyze the changes from baseline over time and at Weeks 17 and 21 for the outcomes of the assessments/questionnaires, the following variables will be analyzed:

- Peak pruritus assessed by numeric rating scale (NRS): scale of the worst itch (from 0 ("no itch") to 10 ("Worst itch imaginable")).
- Eczema and severity index (EASI): composite index ranging from 0 to 72 calculated as follows. The intermediate and total EASI scores will be derived, however, only the total EASI score will be analyzed.
 - Severity scores: for each region (Head and neck, Trunk, Upper limbs and Lower limbs), the severity score will be derived as follows, ranging from 0 to 12:

$$\text{Severity score}_R = \text{Intensity score}_{\text{Erythema}, R} + \text{Intensity score}_{\text{Edema/Papulation}, R} + \text{Intensity score}_{\text{Excoriation}, R} + \text{Intensity score}_{\text{Lichenification}, R},$$

where R = region.

- Region scores: for each region, the region score will be derived as follows:

$$\text{Region score}_R = \text{Severity score}_R * \text{Area score}_R * \text{Multiplier}$$

where R = region, Multiplier = 0.1 for Head and Neck region, 0.3 for Trunk, 0.2 for Upper Limbs, 0.4 for Lower Limbs.

- Total EASI score will be derived as the sum of the 4 region scores.

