- Scoring Atopic Dermatitis (SCORAD): intermediate SCORAD scores (A/B/C) and total SCORAD score calculated as follows. The intermediate and total SCORAD scores will be derived, however, only the total SCORAD score will be analyzed.

$$\text{SCORAD score} = A/5 + 7*B/2 + C, \text{ where}$$

A is the sum of each extent of AD (Left and Right Lower Limbs, Left and Right Upper Limbs, Anterior Trunk, Head and Neck, Genitalia and Posterior Trunk) in %;

B is the sum of severity scales of each symptom of AD (Dryness, Edema/Papulation, Erythema, Excoriation, Lichenification and Oozing/Crust) (scale from 0 to 3);

C is the sum of visual analogue scale (VAS) of itch and sleeplessness (VAS from 0 to 10).

- Investigator global assessment (IGA): 5-point scale to rate the severity of AD globally ranging from 0 (clear) to 4 (severe).
- Patient-Reported Outcomes Measurement Information (PROMIS-itch):
 - Itch-Severity: scores of each of 7 quantitative items and total score.
 - Itch-Activity and Clothing: scores of each item.
 - Itch-Mood and Sleep: scores of each item.
 - Itch-Interference: scores of each item.
 - Itch-Scratching Behavior: scores of each item.
 - Itch-Quality and Itch-Triggers: not applicable (Yes-No answers).
- Patient Oriented Eczema Measure (POEM): total score (sum of the 7 items) ranging from 0 to 28. A high score indicates a high severity.
- Dermatology Life Quality Index (DLQI): total score (sum of the 10 items) ranging from 0 to 30. A high score indicates a poor quality of life (QoL).
- Atopic Dermatitis Control Tool (ADCT): total score (sum of the 6 items) ranging from 0 to 24. A high score indicates a low AD control.
- Sleep Quality NRS: scale of the sleep quality [from 0 (“Worst possible sleep”) to 10 (“Worst pain possible”)].
- Skin Pain NRS: scale of the skin pain [from 0 (“No pain”) to 10 (“Worst pain possible”)].
- Skin Sensitivity NRS: scale of the skin sensitivity [from 0 (“Normal”) to 10 (“Extremely sensitive”)].
- Skin Burning NRS: scale of the skin burning [from 0 (“Not at all”) to 10 (“Very much”)].

To analyse the proportion of AD participants reaching pruritus NRS ≥ 4 point improvement from baseline at Weeks 3, 7, 11, 15, 17 and 21 for each NRS scale (Sleep Quality, Skin Pain, Skin Sensitivity and Skin Burning), a participant will be considered to reach a pruritus NRS ≥ 4 point improvement at a given time point if he presents a change from baseline ≥ 4 at the timepoint.

1.2.6.3 *Exploratory endpoints*

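### Secondary itch, EASI, SCORAD and PRO scores: post-rescue visits are kept or dropped by biopsy impact, the all-treated run is optional, and no analysis counts rescue as non-response

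*Protocol*

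**What the plan says.** - **Analysis set.** Protocol 9.4.7 states: "The analysis of the efficacy markers will be based on the mITT population". Table 4 repeats this for the clinical and PRO scores and for the itch responder percentage.
- **Visit rule.** Protocol 9.3, Table 3, defines mITT as all ITT participants. If prohibited AD therapy is used and is "assessed by the study team as having a significant impact on skin biopsy assessment, only visits prior to rescue treatment use are considered". No separate criterion is given for itch, EASI, SCORAD or the questionnaires.
- **Rescue.** Protocol 6.5.1 allows rescue at the investigator's discretion and explains medical need as "to control intolerable AD symptoms on face and genital areas", with high-potency topical corticosteroids as the treatment named. "The date and time of rescue medication administration" must be entered in the eCRF. SAP 1.2.5 plans a listing of rescue medications.
- **Biopsy site.** Protocol 1.3, footnote e: "Preferably in the forearms followed by back".
- **Sensitivity analysis.** Protocol 9.4.7 commits to an ITT analysis for the primary endpoint. For secondary endpoints it is only a possibility, should rescue use turn out to be important.
- **Imputation.** Protocol 9.4.6 would impute values removed because of rescue if a significant number of patients (for example, more than 20%) used it, and leaves the method to the SAP. SAP 1.2.6 then rules out imputation in the efficacy analyses.

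**The concern.** A rule written to protect the biopsy read-out also decides which clinical and patient-reported scores are analysed. Two participants whose itch improved equally after rescue can be handled in opposite ways, because the study team judged the biopsy affected in one and not in the other.

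With a single arm, no comparator offsets the influence of rescue on the responder percentage or the mean changes. Keeping post-rescue scores and counting rescue as non-response are both legitimate, but they answer different questions. The planned mITT result can fall between them, at a point set by biopsy judgements. The only planned analysis that would give a clean as-observed answer may not be run. The rescue-as-non-response answer is not planned at all.

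**Working it through.** **1. Does the biopsy criterion track the clinical scores?** Set the instruments beside the rescue sites.

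- Itch NRS (Protocol 8.1.1.1) asks "how would you rate your itch at the worst moment during the previous 24 hours" and names no body site.
- SCORAD extent (SAP 1.2.6.2) sums areas that include "Anterior Trunk, Head and Neck, Genitalia and Posterior Trunk".
- EASI (SAP 1.2.6.2) uses "Multiplier = 0.1 for Head and Neck region". With a maximum severity of 12 and area score of 6, that region contributes at most 12 × 6 × 0.1 = 7.2 of 72 points. This is a ceiling, not an expected rescue effect.

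Topical rescue to the face can therefore change all three scores, and rescue to the genital area at least itch and SCORAD, without reaching a forearm or back biopsy. In that case the trigger does not fire and the post-rescue scores stay in.

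**2. When do the protocol and SAP differ on imputation?** 20% of 34 = 6.8, so the protocol's example threshold is passed at 7 rescued (7/34 = 20.6%). Up to 6, neither document imputes. From 7, the protocol would impute removed values and the SAP would not.

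**3. What is the itch responder denominator?** Table 4 says only that the percentage is based on mITT. Since mITT is all ITT participants, this can mean all treated. With removed visits and no imputation, it can also mean observed cases. The rule in SAP 1.2.6.1 that counts only evaluable participants is for nerve-fibre branching. The responder sentence in SAP 1.2.6.2 names the sleep, pain, sensitivity and burning scales. It defines response by the change at the time point, with no rescue condition and no denominator.

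**4. How far can the choice move the rate?** The plan has no figure to reproduce: it gives neither a rescue rate nor a response rate. The counts below are assumptions, with 34 treated and every score available. Let k be the number rescued and r the responders among the other 34 − k.

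- Rescue as non-response: r/34.
- Post-rescue scores kept: r/34 (no rescued participant responds) to (r + k)/34 (all respond).
- Each rescued participant who still improves by ≥ 4 points adds 1/34 = 2.9 points to the kept result.

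| k | r of the others | Rescue as non-response | Post-rescue scores kept |
|--|--|--|--|
| 3 | 16 of 31 | 16/34 = 47.1% | 47.1% to 19/34 = 55.9% |
| 7 | 14 of 27 | 14/34 = 41.2% | 41.2% to 21/34 = 61.8% |
| 10 | 12 of 24 | 12/34 = 35.3% | 35.3% to 22/34 = 64.7% |

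Now take the plan as written with k = 7 and suppose the trigger fires for 3, so that 4 are kept:

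- Observed cases: 14/31 = 45.2% to 18/31 = 58.1%.
- All treated: 14/34 = 41.2% to 18/34 = 52.9%.

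If the trigger fires for all 7, the rate is 14/27 = 51.9% on observed cases and 14/34 = 41.2% on all treated. Even on the all-treated reading, rescue counts as non-response only where the biopsy trigger fires.

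**The case against.** **The study is exploratory and descriptive.** Protocol 9.1 predefines no hypothesis test, so no error rate is at risk. This stands, and it limits the point to interpretation.

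**An as-observed analysis is foreseen.** The ITT set includes every treated patient and has no visit rule, so it would keep the post-rescue scores. A reader might infer that the plan offers no such analysis. That would be wrong: Protocol 9.4.7 names it, but only as an option for secondary endpoints.

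**The biopsy criterion is not irrelevant to the clinical scores.** A reader might infer that visits are removed on grounds with no bearing on itch or EASI. The documents do not support that. The prohibited list in Protocol 6.5.2 includes systemic immunosuppressants, and a therapy that alters the biopsy may well alter itch too. Table 4 also correlates biopsy and clinical changes on mITT, where one common visit set is coherent. What remains is that the two effects need not coincide, and topical rescue to the face or genital area shows how they can differ.

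**The change on imputation is disclosed.** It stands under the SAP's heading for modifications from the protocol. That is correct, although no reason is given.

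**The rate could be rebuilt by hand.** With 34 participants, the rescue listing and individual data listings would allow it. A listing is still not a planned analysis, and the reader would have to choose the denominator.

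**Conclusion.** The point holds for the secondary clinical and PRO endpoints, and it should be corrected. The mITT rule can treat rescued participants inconsistently in a single-arm result. The analysis that keeps every value is optional, and none counts rescue as non-response.

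The size is unknown because the rescue rate is unknown. In the assumed case of 7 rescued, the itch rate is 41.2% with rescue as non-response and 41.2% to 61.8% with post-rescue scores kept. A reader might infer a 20-point inflation from this. The documents do not support that: the upper end needs every rescued participant to respond, although Protocol 6.5.1 reserves rescue for IGA 4 or intolerable symptoms.

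A reader might also infer that the reported itch rate would be meaningless, or that the nerve-fibre primary endpoints are affected. Neither follows. With little rescue the results nearly coincide, and for the biopsy endpoints a biopsy-impact criterion is at least aimed at the right measurement.

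**What to change.** 1. **Visit rule.** Apply the biopsy-impact trigger to biopsy endpoints only. For clinical and PRO scores, make the as-observed summary in all treated AD participants (the ITT set of Protocol 9.4.7) a firm analysis. State in the SAP that the imputation in Protocol 9.4.6 then does not apply to these scores, since no visit is removed. Keep the mITT visit set for both sides of the biopsy-clinical correlations in Table 4.
2. **Itch responders (≥ 4 points).** Add one supplementary table with all treated AD participants as denominator. Count all visits after the first AD rescue as non-response, and likewise scores missing without rescue. Place it beside the as-observed result and state both denominators.
3. **Wording.** Reconcile the mITT row, which speaks of prohibited therapies but cites Section 6.5.3 (headed as permitted medications), with Section 6.5.2 and with its own reference to rescue. Reconcile also the appearance of topical corticosteroids in both 6.5.1 and 6.5.2. No view is taken on the clinical rule.

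**Cost.** SAP wording and one table. No new data are needed: rescue date and time are already recorded and rescue is flagged for the listing. The supplementary rate cannot exceed the as-observed rate on the same denominator. It is strict, since a single early rescue counts through Week 21, which is why it belongs beside the as-observed result and not in its place.
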